12.3 IMPLICATIONS FOR TRIAL DELIVERY DURING COVID-19 PANDEMIC

During the COVID-19 pandemic we will adhere to local NHS Trust protocols for the treatment of outpatients across the participating Dental Hospitals. Wherever possible face-to-face trial appointments will be minimised and we will adhere to local best practice recommendations; this may include telephone / video-conferencing consultations and mail outs (this could include denture provision). Adjustments to dentures can be made at the participant's request if necessary. Trial-specific working instructions will be regularly updated to comply with local NHS Trust guidelines in order to maintain participant safety at all times during COVID-19.

13. ASSESSMENT AND DATA COLLECTION

The study consists of a minimum of nine dental hospital visits for each patient known as "scheduled events". Participants are expected to request extra visits during the denture construction and adjustment stages ("unscheduled events"). Participants will be encouraged to request extra visits if needed at any time throughout the course of the study; therefore the total number of visits will be varied.

Study data will be recorded by research staff on Case Report Forms (CRFs). After each clinic the local research team will post the original paper CRFs to DenTCRU at the University of Leeds. When all local approvals to run this study are obtained, details on the schedule of CRFs, data to be collected and guidance on the completion of CRFs will be given to the site research staff at the site initiation visit and to new staff trained by the person appointed by the local site PI.

The digital scan images will be produced locally at each research site and pseudonymised with the participant's individual study ID number. The study team based in the digital dental laboratory at the University of Leeds will remotely dial into the scanning equipment at the remote sites via a secure encrypted connection. The Leeds digital lab team will then download the scanned images into a Zip folder held on a password protected computer in a locked lab. These images will then be processed using bespoke in-house software in order to assemble a master scan file.

Each research site will be expected to maintain a file of essential study documentation (Investigator Site File) and keep copies of all completed CRFs for the study. Within the local

Investigator Site File, the Recruitment Log will record the individual participant study ID number allocated to each participant against the participant's name, and personal details. Once allocated a study number, all subsequent CRFs will only identify the participant by their individual participant study ID number, their initials and date of birth.

13.1 SCHEDULE OF EVENTS

	Stage Screening	Screening	ening Impressions		Denture Construction		Initial Habituation & Assessment Period (IHAP)	Adjustment Periods		Confirmation Period	
	Visit		1	2	3	4	5	6	7	8	9
	Week	-1 to 1	1	3	5	7	9	11	19	27	29
Research activities	Appointments		1 st Imps	2 nd Imps	Jaw reg	Wax try-in	Fit	Review	After 8 weeks	After 8 weeks	After 2 weeks
Screening eligibility criteria		~									
Informed consent & Registration			1								
Randomisations							✓	✓			
OHIP Edent			✓						✓	✓	
5-Point Likert Assessment of dentures								*	*	*	>
Participant Preference Assessment of dentures								~		8	~
Participant Diary							1	✓			
Adverse events			1	1	1	1	1	✓	✓	√	✓

13.2 ASSESSMENTS

The primary purpose of this pilot study is to calculate the sample size needed for a full RCT using the primary outcome (which is the participant's preference for the dentures before they are adjusted). In addition to the assessment of the primary outcome, the secondary outcome measures (of the future RCT) will also be investigated here in the pilot RCT. Thus, this is a full protocol pilot study and it is anticipated that the data collected here may be combined with that collected in the planned future trial.

The NIHR provide a useful definition for both "Pilot" and "Feasibility" studies. (See: <a href="https://www.nihr.ac.uk/funding-and-support/documents/funding-for-research-studies/research-studie

programmes/RfPB/Guidance%20Documents/Guidance on feasibility studies.pdf). Under these definitions, this is a full protocol pilot study, "a version of the main study that is run in miniature"

Please read this section in conjunction with the Study Flow Diagram in Section 3b.

The assessments, listed in the order in which they are used, are:

13.2.1 BASELINE ORAL HEALTH IMPACT PROFILE (OHIP-EDENT)

Timing: at Clinical Visit 1

OHIP-EDENT is a validated questionnaire specifically designed to assess edentulous participants' quality of life. The OHIP-EDENT questionnaire is widely used in the prosthodontic literature (1273 publications to date). This baseline will allow the assessment of any improvement/deterioration in the participants' quality of life through the provision of dentures. Statistical plan for the analysis of OHIP-EDENT scores is detailed in Section 14.4.

13.2.2 PARTICIPANT DIARY

Timing: after Clinical Visit 5

During the two-week Initial Habituation and Assessment Period each participant is given a diary. The diary has two purposes. Firstly, it is to instruct them as to when to wear each of the dentures. The order in which the dentures are worn is randomised. Although a carryover effect is not anticipated, this initial randomisation limits any possible period effect (and allows any carryover period effect to be assessed). The second reason for the diary is to allow the participant to make notes of difficulties and/or benefits of wearing each denture. Previous experience of this protocol has shown that the participants benefit from referring to their diary when answering the questionnaire in the assessments below.

13.2.3 PARTICIPANT PREFERENCE FOR THE DENTURES BEFORE ADJUSTMENT

Timing: at Clinical Visit 6

Participant preference before adjustment has been chosen to be the primary endpoint because it is the driving motivation to ascertain which method of denture manufacture is most acceptable to the participant prior to subsequent denture adjustment. (See Section 14 Statistical Analysis)

13.2.4 PARTICIPANT ASSESSMENT OF THE COMFORT STABILITY AND CHEWING EFFICIENCY OF EACH DENTURE

Timing: at Clinical Visit 6

After the two-week Initial Habituation and Assessment Period each participant is asked to score the two dentures using 5 point Likert scale assessing the three domains of Comfort, Stability and Chewing Efficiency.

See Section 14.3 for the statistical analysis plan for these Likert scales.

There is a second randomisation at this point to decide which denture is worn during the first eight-week Adjustment Period.

13.2.5 OHIP-EDENT AFTER THE FIRST EIGHT-WEEK ADJUSTMENT PERIOD

Timing: at Clinical Visit 7

The participants are asked to wear one denture for eight weeks. During those eight weeks they are encouraged to return for any adjustments that they require.

After the participant has worn the dentures for eight weeks, they will be asked to re-assess their quality of life though the OHIP-EDENT questionnaire. See Section 14.4 for the statistical analysis plan for the OHIP-EDENT questionnaires.

13.2.6 OHIP-EDENT AFTER THE SECOND EIGHT-WEEK ADJUSTMENT PERIOD

Timing: at Clinical Visit 8

After Clinical Visit 7 the participant is asked to wear the second denture for an eight-week adjustment period (randomised for denture order). During those eight weeks they are encouraged to return for any adjustments that they require.

After the participant has worn the dentures for eight weeks, they will be asked re-assess their quality of life though the OHIP-EDENT questionnaire. See Section 14.4 for the statistical analysis plan for the OHIP-EDENT questionnaires.

13.2.7 PARTICIPANTS' ASSESSMENT OF THE COMFORT, STABILITY AND CHEWING EFFICIENCY OF DENTURES OF BOTH DENTURES

Timing: at Clinical Visit 9

After the two Adjustment Periods the participants take both set of dentures away for the two-week Confirmation Period. On their return at Clinical Visit 9 they will be asked to assess both dentures for comfort stability and chewing efficiency.

See Section 14 for statistical analysis of this assessment.

13.2.8 PREFERENCE FOR ADJUSTED DENTURES

Timing: at Clinical Visit 9

After the two Adjustment Periods the participants take both set of dentures away for the two-week Confirmation Period. During these two weeks they use the dentures as they wish. When they come back at Clinical Visit 9 they assess which set of dentures they prefer. See Section 14 for statistical analysis of this assessment.

13.3 DEFINITION OF THE END OF THE STUDY

The end of the study is defined as the date of the last participant's final assessment visit at the end of the Confirmation Period.

14. STATISTICAL ANALYSIS

14.1 CALCULATION OF SAMPLE SIZE FOR A DEFINITIVE RCT

The results from this study will be used for sample size calculation for a definitive RCT if a preference difference is found between conventional denture and 3-D printed denture. The unadjusted proportion discordance will be retained for this study and a discordant difference of 0.1 will be used to calculate the sample size using McNemar's test.

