7. AIMS AND OBJECTIVES

The overarching aim of this research programme is to significantly impact on the quality of denture production within NHS dentistry. To achieve this objective, we aim to provide evidence of effectiveness and cost effectiveness of 3-D printing dentures. This current study sits within this extensive research programme (outlined in Section 3a.).

The specific aim of this pilot RCT is to determine the sample size to be used in the definitive future RCT study.

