7.1 PRIMARY OBJECTIVE

The primary objective for this pilot RCT is to compare 3-D printed and traditional dentures in order to enable a sample size calculation for a future RCT.

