7.3 PRIMARY RESEARCH QUESTION

What would be the required sample size for a full protocol RCT which investigated the participants' preference for 3-D printed dentures or conventional dentures?

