10. RECRUITMENT AND REGISTRATION

10.1 RECRUITMENT

The recruitment target requires that 18 participants are recruited over a period of six months. Participants will be recruited from the routine clinics and/or waiting lists for replacement of complete dentures at Leeds Dental Institute (LDI), the University Dental Hospital of Manchester, and Birmingham Dental Hospital.

The proposed outcome measures (see Section 7.2) have not been used to investigate 3-D printing of dentures before. This causes a significant issue for calculating the sample size for the future grant funded RCT.

In estimating the number of cases we will need, we have looked at previous use of cross over RCTs in denture studies. The estimated number of cases needed is 18. **Please note:** although calculated using the best evidence, this is essentially an empirical estimate.

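### Section 14.1 makes the definitive-trial sample size conditional on an undefined preference difference, although section 7 states that aim without condition and the calculation does not need one

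*Protocol*

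**What the plan says.** Protocol section 7 states the purpose without qualification: "The specific aim of this pilot RCT is to determine the sample size to be used in the definitive future RCT study". The primary objective in 7.1 is to "compare 3-D printed and traditional dentures in order to enable a sample size calculation for a future RCT", and the research question in 7.3 opens "What would be the required sample size for a full protocol RCT". Section 13.2 repeats that sizing the full trial is the primary purpose, using preference before adjustment, which is recorded at Visit 6.

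Section 14.1 then says the results will be used for "sample size calculation for a definitive RCT if a preference difference is found between conventional denture and 3-D printed denture". Its next sentence names the inputs: the discordance for the unadjusted dentures is kept, and "a discordant difference of 0.1 will be used to calculate the sample size" with McNemar's test. Section 14.2 gives McNemar's test as the analysis of preference. Neither section says what counts as finding a difference, gives a significance level, or says what happens if no difference is found.

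On size, section 10.1 says: "The recruitment target requires that 18 participants are recruited over a period of six months". It adds that "although calculated using the best evidence, this is essentially an empirical estimate".

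**The concern.** A pilot whose single stated purpose is to deliver a sample size should not carry a rule that can withhold it. Section 14.1 contains such a rule, while sections 7, 7.1, 7.3 and 13.2 contain none. The text therefore disagrees with itself about when the primary objective is met.

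The rule also has no role in the arithmetic. The target difference is set in advance at 0.1, and the only quantity taken from the pilot is the proportion of participants who prefer one denture over the other in either direction. Whether those preferences lean one way does not matter to the calculation.

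Three things are at stake:
- the primary objective may go unanswered;
- because the trigger is undefined, whether it was met can be decided after the data are seen;
- if the trigger is a significance test, the discordance carried forward comes from a selected set of pilots.

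**Working it through.** **Inputs from the protocol.** Pilot size 18 (10.1, no dropout allowance stated). Design difference for the definitive trial d = 0.1 (14.1). McNemar's test (14.1, 14.2). The 18 has no stated power, level or effect size, so there is no figure of the plan's own to reproduce.

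**Assumptions, because the protocol gives no value.** Two-sided 5% level; 80% power for the definitive trial; true discordance ψ anywhere from 0.1 to 1.0; true difference in the pilot equal to the 0.1 design value.

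**Step 1: does the calculation need an observed difference?** The usual paired-proportion formula is

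N = [1.96·√ψ + 0.842·√(ψ − d²)]² / d².

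At ψ = 0.5 and d = 0.1: [1.96 × 0.7071 + 0.842 × 0.7]² / 0.01 = (1.386 + 0.589)² / 0.01 ≈ 390.1, so 391 participants. The observed preference difference appears nowhere. A pilot with 5 preferring each denture gives the same N as one with 10 preferring one and 0 the other.

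**Step 2: how often is the condition met?** Let D be the number of discordant participants, D ~ Bin(18, ψ), and b the number of these favouring one denture, b | D ~ Bin(D, (ψ + 0.1)/(2ψ)). Summing over all outcomes:

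| ψ | Exact McNemar p ≤ 0.05 | Uncorrected chi-square p ≤ 0.05 | Any imbalance | Mean discordance if exact test passed | N at true ψ |
|---|---|---|---|---|---|
| 0.1 | 0.6% | 9.8% | 85% | 0.35 | 77 |
| 0.2 | 2.2% | 13.0% | 86% | 0.36 | 155 |
| 0.3 | 3.6% | 11.2% | 87% | 0.40 | 234 |
| 0.5 | 4.5% | 7.8% | 89% | 0.53 | 391 |
| 0.8 | 4.3% | 7.2% | 91% | 0.82 | 626 |
| 0.9 | 5.0% | 7.5% | 91% | 0.91 | 705 |
| 1.0 | 4.6% | 4.6% | 83% | 1.00 | 783 |

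The mid-p version gives 2.8% to 7.9% and the continuity-corrected version 0.6% to 4.6%. Under the significance reading the calculation is therefore not triggered in at least 87% of pilots. Under the any-imbalance reading it is withheld only at an exact tie, in 9% to 17% of pilots (100 − 91 and 100 − 83).

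**Step 3: what can 18 participants show?** The smallest split reaching p ≤ 0.05 is 6 v 0 with the exact test (2 × 0.5⁶ = 0.031), an observed difference of 6/18 = 0.33. With the uncorrected chi-square it is 4 v 0 (4²/4 = 4.0, above 3.84), or 4/18 = 0.22. Both exceed 0.1. For about 80% power with the exact test the true difference would need to be about 0.46, 0.50, 0.59 or 0.65 at ψ = 0.5, 0.6, 0.8 or 1.0.

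**Step 4: effect of selection on the retained discordance.** At ψ = 0.3, pilots that pass the exact test have mean discordance 0.40, which moves N from 234 to 309. With the uncorrected chi-square the mean is 0.32. At ψ = 0.5 or above the exact-test shift is 0.03 or less.

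**Step 5: size of ordinary sampling error.** If 9 of 18 are discordant, the exact 95% interval for ψ is 0.26 to 0.74, and N runs from 202 to 579 around 391. This is larger than the selection effect at ψ = 0.3 and is present whether or not the condition is kept.

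**The case against.** The strongest reply is that the protocol never equates finding a difference with statistical significance. Section 14.1 attaches no test or level to the condition, and 14.2 does not link its McNemar test to it. A reader might infer that the pilot will most likely fail to answer its own question. That follows only on the significance reading. On the any-imbalance reading the condition is usually met and the conclusion reverses. This part of the reply stands, and the low trigger rates must be read as conditional.

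Nor is 0.1 a difference planned or expected in the pilot; it is the design value for the definitive trial. With larger true differences the exact test passes more often: 19% to 47% at a true difference of 0.3 (discordance 1.0 down to 0.3), and 95% when difference and discordance are both 0.5. This also stands.

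The second sentence of 14.1 carries no condition, so the first could be a loose statement of intent to proceed only if there is a preference worth pursuing. That is possible, but progression and calculation are different decisions, and the text ties the condition to the calculation.

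The selection bias is material only at low discordance, and the protocol gives no planning value for it. Finally, no data are lost: the Visit 6 discordance is collected in any case and N could be computed from it. That limits the severity but does not remove the contradiction with section 7. A definition of the trigger in the SAP could settle the ambiguity, but not the lack of need for the condition.

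**Conclusion.** The point holds as an internal contradiction and an unnecessary, undefined condition on the primary objective. Neither reading gives the clause a useful function. Read as significance, it triggers the calculation in at most about 13% of pilots (about 5% or less with the exact test), and it inflates the retained discordance when that is low: 0.30 becomes 0.40 with the exact test, with little bias at 0.5 or above. Read as any imbalance, it is met in 83% to 91% of pilots and withholds a calculation that the data fully support in the remaining 9% to 17%.

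These figures rest on 18 evaluable participants, a two-sided 5% level, a true difference equal to the 0.1 design value and discordance between 0.1 and 1.0; only the 18 and the 0.1 come from the protocol. The documents do not support saying that the pilot will probably fail, nor that a non-significant result would be reported as no preference. Severity: should-fix.

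**What to change.** In section 14.1:
- Delete the conditional clause at the end of the first sentence.
- State that the definitive sample size will be calculated from the Visit 6 discordance and the fixed difference of 0.1, whatever preference is observed.
- Report the preference difference with a 95% CI, and N across the confidence interval for the discordance.
- State that the pilot's McNemar p-value is descriptive and does not decide whether the calculation is done.

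If the SAP carries the same condition, it needs the same change. The cost is a few sentences of text, with no extra participants, visits or data.

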14.2 UNADJUSTED AND ADJUSTED DENTURE PREFERENCE (13.1.3 and 13.1.8 above)

The outcome of preference for unadjusted dentures and the secondary outcome of preference for adjusted denture will be presented as a 2x2 table for paired data and analysed using McNemar's test for paired data.

		3-D printe	nted denture		
		Prefer/satisfactory	Not prefer/unsatisfactory		
Conventional	Prefer/satisfactory	Number with no preference (like both)	Number who prefer denture produced conventionally		
denture	Not prefer/unsatisfactory	Number who prefer denture produced by 3-D printing	Number with no preference (dislike both)		

14.3 STATISTICAL ANALYSIS OF REPEATED LIKERT SCALES (13.1.4, and 13.1.7 above)

Differences between Likert scores (measuring comfort, stability and chewing efficiency) for each denture will be calculated and compared using the Wilcoxon test for matched pairs. Likert scores will be presented by a p-value based on a Wilcoxon Test score. Scores will be compared between conventional and 3-D printed dentures at the end of Habituation/Assessment Period and the Confirmation Period.

Summary statistics and frequency distributions will also be presented for each denture for two time points. In addition summary statistics and frequency distributions will be presented for the difference between the two dentures.

14.4 STATISTICAL ANALYSIS PLAN FOR THE OHIP-EDENT QUESTIONNAIRE (13.1.5 and 13.1.6 above)

Overall OHIP-EDENT scores at the end of each Adjustment Period (i.e. by period) will be analysed using an ANOVA model appropriate for an AB/BA cross-over design. Domain scores and overall OHIP-EDENT scores will be presented as summary statistics and frequency distributions by period and overall. The model will incorporate denture as a fixed effect and participant as a random effect. Participant effects will be treated as random

effects in the model since participants will be randomly selected (ref). (The mean difference in OHIP-EDENT between the dentures will be estimated with 95% confidence intervals.)

Normality checks will be made on the OHIP-EDENT distribution. Additionally, a normality check on the residuals from the model described above will be made. Both normality checks will be done using a normal QQ-plot.

There is a possibility of a period effect, and as such a period effect t-test will be performed. Although a carryover effect is not anticipated, a carryover t-test will also be performed to test for carryover. If such effects are shown to be statistically significant, then the model will incorporate these effects (both as fixed effects).

Baseline will not be included in the model since when subtracting each participant's baseline from both outcome measurements, the effect of the baseline totally disappears and the cross-over differences would be just the same if baseline had never been used (ref).

OHIP-EDENT scores will be presented by mean difference between dentures with 95% confidence intervals.

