11.2 SECOND RANDOMISATION

The aim of the second randomisation is to establish the order of testing during the two 8-week Adjustment Periods. This second randomisation will occur at the conclusion of the Initial

Habituation and Assessment Period to determine the colour re-marking (red or green) of the dentures; half the 3-D printed dentures will be coded one colour (green), as will half the conventional dentures. Similarly, half the 3-D printed dentures will be coded the other colour (red), as will half the conventional dentures. This colouring process will again be performed by laboratory staff at each participating site and the dentist asking the participants to wear the red colour-coded dentures first. This second randomisation will be balanced for order of testing in the Initial Habituation and Assessment Period.

The Second Randomisation CRF must be completed, a copy must be retained by the laboratory staff at the sites and the original must be returned by post to DenTCRU to provide evidence that randomisation has taken place.

Careful records are needed to keep track of the colour coding and randomisation allocation. In this way the participants and the clinical members of the study team at each research site are kept blind to the colour coding; they do not know which denture is being assessed. Unblinding will only be performed once all clinical assessments for all participants have been completed.

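### Section 14.4 lets a carry-over pre-test change the OHIP-EDENT model, so the 95% interval for the denture difference no longer has its stated coverage

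*Protocol*

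**What the plan says.** The order of dentures in the Adjustment Periods comes from the second randomisation (section 11.2): "The aim of the second randomisation is to establish the order of testing during the two 8-week Adjustment Periods". Allocation is half and half: "half the 3-D printed dentures will be coded one colour (green), as will half the conventional dentures". The target in section 10.1 is 18 participants.

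For the overall OHIP-EDENT score, section 14.4 starts from this model: "The model will incorporate denture as a fixed effect and participant as a random effect". On period it says: "There is a possibility of a period effect, and as such a period effect t-test will be performed". It adds a carry-over t-test while stating that no carry-over is expected. It then gives the conditional rule: "If such effects are shown to be statistically significant, then the model will incorporate these effects (both as fixed effects". No significance level is set for these tests. Baseline is left out on the ground that "the effect of the baseline totally disappears and the cross-over differences would be just the same if baseline had never been used". The result is to be reported as a mean difference between dentures with a 95% confidence interval.

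**The concern.** In a two-period, two-sequence design, carry-over is confounded with the difference between sequence groups. A term for carry-over into period 2 can be fitted only by giving up the within-participant comparison for the denture effect, which is the reason for using a cross-over at all. The test that triggers this switch uses largely the same information as the estimate it switches to. A chance imbalance between the sequence groups therefore tends to produce both a significant carry-over test and a large denture difference, and an interval computed as if the model had been fixed beforehand is too optimistic.

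What is at stake is the reported OHIP-EDENT difference and its interval. Section 13.2 says that the secondary outcomes of the future trial are investigated here and that the data may be combined with that trial, so the rule could also carry forward.

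**Working it through.** **Inputs.** 18 participants (section 10.1) and half-and-half order (section 11.2) give 9 per sequence if all complete; the 9 is derived, not printed. The 18 itself cannot be reproduced: no SD, effect size, alpha or power is given, and section 10.1 says "although calculated using the best evidence, this is essentially an empirical estimate". The protocol gives no pre-test level, within-participant correlation (rho) or SD. Assumed: two-sided pre-tests at 5% (10% as a second case), rho from 0 to 0.9, total SD = 1.

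**What the denture coefficient estimates.** Let D1 and D2 be the differences in mean score between the sequence groups in periods 1 and 2, tau the denture effect and lambda the difference in carry-over. Then D1 estimates tau and D2 estimates -tau + lambda.
- Within-participant estimate: (D1 - D2)/2, which estimates tau - lambda/2.
- Carry-over contrast: D1 + D2, which estimates lambda.
- Denture effect adjusted for carry-over: (D1 - D2)/2 + (D1 + D2)/2 = D1.

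Mixed models fitted to one simulated data set of 18 agree. The within-participant difference was 0.137 and the first-period difference 1.026. The denture coefficient was 0.137 with denture alone or with period, and 1.026 once a period-2 carry-over term was added, with or without period. With carry-over entered only as a sequence main effect, it stayed at 0.137.

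**Link between test and estimate.** corr(D1, D1 + D2) = sqrt((1 + rho)/2): 0.71 at rho 0, 0.87 at 0.5 and 0.97 at 0.9.

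**Precision.** Variance within participants = 2(1 - rho)/18; first-period variance = 2/9. The SE ratio is sqrt(2/(1 - rho)).
- rho 0.5: 0.471 v 0.236 SD, ratio 2.0.
- rho 0.7: 0.471 v 0.183 SD, ratio 2.6.

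At rho 0.5, matching the cross-over's precision needs 4/n = 1/18, so n = 72 participants.

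**Error rate of the whole rule.** Simulation with 9 per sequence, all effects null, 400,000 trials per setting:

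| rho | 5% pre-tests | 10% pre-tests |
|---|---|---|
| 0 | 6.5% | 7.1% |
| 0.3 | 7.0% | 7.7% |
| 0.5 | 7.5% | 8.4% |
| 0.7 | 7.9% | 8.9% |
| 0.9 | 8.8% | 9.5% |

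Among trials with a falsely significant carry-over test (5% of them at the 5% level), the denture test rejects in 31% at rho 0, 51% at 0.5 and 78% at 0.9. Pre-testing period alone gives 5.1% to 5.3%.

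These figures fit together by hand. Participant sums and differences are independent, so total error = 0.05 x (rate in the carry-over branch) + 0.95 x (rate otherwise, about 5.2%):
- rho 0: 0.05 x 0.31 + 0.95 x 0.052 = 0.065
- rho 0.5: 0.05 x 0.51 + 0.95 x 0.052 = 0.075
- rho 0.9: 0.05 x 0.78 + 0.95 x 0.052 = 0.088

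With denture and period always fitted and no pre-test, simulated error is 5.0% at every rho, including with a true period effect of 0.2 to 1 SD.

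**Baseline.** (Y1 - b) - (Y2 - b) = Y1 - Y2, so baseline cancels within a participant. D1 compares different participants, so the cancellation on which section 14.4 relies does not occur in the carry-over branch.

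**Period.** Never fitting a true 0.5 SD period effect at rho 0.5 with 9 v 9 gives a type I error of 2.9%: the interval is too wide, not too narrow. Bias appears only if the sequences become unbalanced. It is the period effect times (n1 - n2)/(n1 + n2); an assumed 9 v 6 would give 0.5 x 3/15 = 0.10 SD.

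**The case against.** Several points on the other side stand.

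- **Importance.** The aim is a sample size for the definitive trial (section 7), calculated from preference discordance with McNemar's test (section 14.1). The primary outcome is preference before adjustment (section 13.2.3). No OHIP-EDENT quantity enters either. A reader might infer that the pilot's main result is compromised; the protocol does not support that.
- **Coding.** Section 14.4 says only that carry-over enters as a fixed effect. A reader might infer that the model must collapse to a first-period comparison. That holds for a period-2 carry-over term, the usual meaning, but not for a sequence main effect, which leaves the denture estimate within-participant. In that case, however, the carry-over test does nothing for the denture estimate, which is no argument for keeping it.
- **Period.** A reader might blame both pre-tests equally. The figures do not bear this out: the period step adds at most about 0.3 percentage points when sequences are balanced. The two-week habituation period with both dentures (section 8) also makes a large period effect less likely, without excluding one.
- **Conditional rates.** The 31% to 78% applies only to the few trials with a false carry-over signal; it is not the error rate of the analysis.

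It cannot be said that the matter is left to a separate analysis plan: the protocol itself fixes the rule.

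**Conclusion.** The rule is wrong as written and should be changed, at moderate priority. Under a period-2 carry-over term and 5% pre-tests, the nominal 95% interval covers about 91% to 93.5%, and down to about 90.5% with 10% pre-tests. When the switch occurs, the true SE is about 2.0 to 2.6 times the cross-over SE at correlations of 0.5 to 0.7. The pre-test level, the correlation and full completion at 9 v 9 are assumptions, but the inflation appears at every correlation tried. If carry-over is entered only as a sequence effect, what remains is a redundant test and the small effect of pre-testing period.

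**What to change.** In section 14.4:
1. Always fit denture and period as fixed effects and participant as a random effect, with no carry-over term.
2. Remove the period and carry-over t-tests as model-selection steps.
3. Report mean scores by sequence and period descriptively, so that a reader can judge carry-over without its changing the model.
4. State that the mean difference and its 95% interval come from this one model.

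The stated reason for omitting baseline then holds for the within-participant contrast. The cost is a change of wording and one degree of freedom for period; no extra data or participants are needed.
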